#### 5.5 PREMATURE TERMINATION OR SUSPENSION OF STUDY

At six month intervals, the study biostatistician ([name]) will test whether there are significant differences in the occurrence of moderate, severe, and serious AEs in the placebo vs. the experimental condition with alpha set at .05. These results will be provided to the Data Safety and Monitoring Board (DSMB) along with the summary report of enrollment.

Administration of study agent will be halted when three serious AEs\* determined to be "probably related" (i.e., with new onset during study patches/pills) are observed. The PI will immediately notify the DSMB when this occurs. The DSMB will notify the study sponsor and investigators immediately when the third severe event is reported and enrollment screens will stop accepting new study participants. [name] will again perform an unblinded statistical analysis to further determine whether active study medication (E2/P4) is significantly related to greater risk of AEs relative to placebo. All requested documentation will be provided to the DSMB. The DSMB will convene an ad hoc meeting by teleconference or in writing as soon as possible. The DSMB will provide recommendations for proceeding with the study to the PI and the NIH. The study sponsor will inform all appropriate regulatory agencies of the temporary halt and the disposition of the study.

The DSMB will consider stopping the entire study based on the results of the statistical tests provided by [name]: specifically, if the experimental hormone stabilization condition is associated with greater risk of severe or serious AEs than placebo, and there is evidence (as determined by [name]) that such AEs are causally related to the study drug, the study

will be terminated.

**\*Notable examples of serious adverse events in the present study include development of a venous thromboembolism or suicide attempt.**

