### 10.4 DESCRIPTION OF STATISTICAL METHODS

#### 10.4.1 GENERAL APPROACH

The design of this study is a two-period crossover design, where each of two study periods is a perimenstrual frame of the menstrual cycle (days +7 to +22 following ovulation where positive ovulation test day=0). Each participant will complete both conditions in a randomized order.

The primary windows of comparison will be the final seven days of each administration phase, which will allow for a comparison of a woman's mean scores in the placebo condition compared to her mean scores in the experimental condition.

Primary hypothesis tests will be evaluated using a alpha level of .05, with a two-tailed test.

All outcomes will be checked for normality; given the low likelihood that suicidality will follow a normal distribution even in this clinical sample, we expect that we will need to utilize nonparametric procedures.

---

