#### 10.4.4 SAFETY ANALYSES

All adverse events will be recorded once per condition for each subject, calculated dichotomously based on its emergence during the treatment timeframe. These outcomes will be presented in tables for review by the DSMB, and such outcomes will be accompanied by descriptive and inferential statistics (both mean levels and change from baseline in each condition) to determine whether AEs and changes in AEs are more likely to occur in the experimental condition.

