#### 10.4.7 PLANNED INTERIM ANALYSES

##### 10.4.7.1 SAFETY REVIEW

At six month intervals, the study biostatistician ([name]) will test whether there are significant differences in the occurrence of moderate, severe, and serious AEs in the placebo vs. the experimental condition with alpha set at .05. These results will be provided to DSMB along with the summary report of enrollment.

Administration of study agent will be halted when three serious AEs\* determined to be “probably related” are observed. The PI will immediately notify the DSMB when this occurs. The DSMB will notify the study sponsor and investigators immediately when the third severe event is reported and enrollment screens will stop accepting new study participants. [name] will again perform an unblinded statistical analysis to further determine whether active study medication (E2/P4) is significantly related to greater risk of AEs relative to placebo. All requested documentation will be provided to the DSMB. The DSMB will convene an ad hoc meeting by teleconference or in writing as soon as possible. The DSMB will provide recommendations for proceeding with the study to the PI and the NIH. The study sponsor will inform all appropriate regulatory agencies of the temporary halt and the disposition of the study.

The DSMB will consider stopping the entire study based on the results of the statistical tests provided by [name]: specifically, if the experimental hormone stabilization condition is associated with greater risk of severe or serious AEs than placebo, and there is evidence (as determined by follow up with [name] using unblinded data provided by [name]) that such AEs are causally related to the study drug, the study will be terminated.

**\*Notable examples of serious adverse events in the present study include development of a venous thromboembolism or suicide attempt.**

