### 10.5 SAMPLE SIZE

An unlimited number of women will be screened. 45 women will be enrolled in the study, with the goal of 30 women completing the study.

Power analyses are described below; alpha is set at .05, power at 80%. The null hypothesis is no link between the study experimental condition and risk for suicidal ideation, intent, and planning; the alternate hypothesis is that hormone stabilization in the experimental condition will prevent flux in these suicide-related outcomes. Because no previous studies have examined the impact of experimental hormones on suicidality, we have conducted power analyses using existing effect sizes on related constructs (e.g., BPD features).

**Power Analysis.** For the contrast testing the primary hypothesis, we will have power to detect a conventionally medium-sized effect of hormone withdrawal ( $r = .30$ ;  $d = .60$ ) at 80% power with just 17 participants. The PI's previous work in women with BPD suggests that attrition could be as high as 25% across two conditions; should attrition be this high, enrollment of 22 participants would be required for adequate power. However, to improve generalizability of our findings and to ensure 80% power to detect small-to-medium effect sizes ( $r = .20$ ;  $d = .40$ ), we aim to include 30 completers (with 45 women randomized). This number is especially reasonable given the

much larger effects found in the candidate's recent studies for the effect of natural ovarian steroid changes (average  $r = .58$ ;  $d = 1.38$ ) on daily symptoms of depression, rejection sensitivity, anxiety, and impulsivity.

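### Adverse events are compared between conditions by .05 tests, with no planned risk difference or confidence interval and no stated power, so a non-significant result is weak evidence of no harm

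*Combined protocol and SAP*

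**What the plan says.** Section 10.4.4 scores each AE yes or no, once per woman per condition. The DSMB receives tables with descriptive statistics for each condition and inferential statistics "to determine whether AEs and changes in AEs are more likely to occur in the experimental condition". That section names no test, no alpha and no measure of the between-condition difference.

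The alpha is in sections 5.5, 8.5 and 10.4.7.1. Every six months the biostatistician tests for "significant differences in the occurrence of moderate, severe, and serious AEs in the placebo vs. the experimental condition with alpha set at .05" and passes the results to the DSMB. Section 5.5 adds: "The DSMB will consider stopping the entire study based on the results of the statistical tests".

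Two-sidedness is stated only for the primary hypotheses (section 10.4.1: "Primary hypothesis tests will be evaluated using a alpha level of .05, with a two-tailed test"). The 80% power in section 10.5 is for the suicidality contrast; no AE comparison is powered. On size, the same section says "45 women will be enrolled in the study, with the goal of 30 women completing the study". Section 10.1 says there will be no formal SAP, so no later analysis document is planned to fill these gaps.

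**The concern.** A significance test answers whether the data are incompatible with no difference. A safety review also needs to know how large an excess the data leave open. With at most a few dozen pairs, a p-value above .05 is the likely result even when active treatment raises the AE rate substantially, and a p-value alone does not show how much harm remains possible. As written, the only inferential comparison of AEs between conditions is such a test, both at the six-monthly reviews and at the end. At stake is what the DSMB and readers of the final report can conclude about moderate and severe AEs when the test is not significant.

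**Working it through.** There is no AE power figure in the plan to reproduce. The check therefore asks what a .05 test could detect at the planned size.

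**Inputs from the protocol.** Alpha .05 (10.4.7.1). Paired data, since "The design of this study is a two-period crossover design" (10.4.1). Binary AE per woman per condition (10.4.4). 30 completers (10.5).

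**Assumptions, not in the protocol.** AE rates of 10% on placebo and 30% on active; a two-sided McNemar test; within-woman correlation ρ from 0 to .3. The protocol lists only single side-effect rates (for example 29% for breast tenderness), not moderate-or-worse AE rates by condition.

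**Step 1: discordant probabilities.** P(AE in both) = .3 × .1 + ρ√(.3 × .7 × .1 × .9) = .03 + .1375ρ.
- ρ = 0: active-only .27, placebo-only .07.
- ρ = .3: P(both) = .0712, so active-only .2288, placebo-only .0288.

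**Step 2: chance of missing the excess with 30 pairs.** The number of discordant pairs m is binomial (30, active-only + placebo-only). Given m, the number b that are active-only is binomial (m, active-only / (active-only + placebo-only)). The exact p-value is 2 × P(Bin(m, ½) ≥ max(b, m − b)), capped at 1. Summing the probability of all outcomes with p > .05 gives:

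| ρ | Exact | Mid-p | Uncorrected |
|---|---|---|---|
| 0 | 64% | 54% | 54% |
| .1 | 61% | 50% | 50% |
| .2 | 58% | 46% | 44% |
| .3 | 54% | 41% | 37% |

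At the highest correlation these rates allow (.51), the exact test still misses 43%. The other two tests fall to 26% (mid-p) and 12% (uncorrected). For 80% power the exact test would need about 71 pairs at ρ = 0 or 52 at ρ = .3.

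**Step 3: early reviews.** The most extreme result with 5 pairs is 5 active-only against 0 placebo-only: exact p = 2 × (1/2)^5 = .063. Six against none gives 2 × (1/2)^6 = .031. So with 5 pairs the exact test cannot reach .05, whatever the rates or correlation. Mid-p could (5 v 0 gives .031), but at ρ = 0 that outcome has probability .27^5 = .0014. With 15 pairs, exact power is 8–9% over ρ = 0 to .3.

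When might those numbers occur? Assume even accrual of 45 women over 20 − 3.5 = 16.5 months, 3.5 months per participant and two-thirds completing. Completers at month 6 are (45/16.5) × 2.5 × 2/3 = 4.5, about 5. At month 12 they are (45/16.5) × 8.5 × 2/3 = 15.5, about 15. The accrual pattern is an assumption.

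**Step 4: what an interval adds.** Suppose 30 women give 6 active-only and 2 placebo-only events. The exact p-value is 2 × (28 + 8 + 1)/256 = .29. The risk difference is 4/30 = +13 points. The Wald interval is .133 ± 1.96 × √(8 − 16/30)/30, or −5 to +31 points. Tango's score interval solves (b − c − nδ)/√(n[2q + δ(1 − δ)]) = ±1.96, with c the placebo-only count and q the constrained estimate of the placebo-only probability. It gives −6 to +33 points. The test says not significant; the interval shows that an excess of 30 points has not been excluded.

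**Step 5: why the method must be named.** With 8 v 2, exact p = .11, yet the Wald interval is +1 to +39 points and excludes zero. The score statistic at zero is (8 − 2)²/10 = 3.6, below 3.84, so a score interval includes zero (−1 to +40).

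**The case against.** A reader might infer three stronger things, and the documents support none of them.

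- **That safety is decided by these tests.** It is not. The DSMB will consider the test results, but termination also needs a judgement that the AEs are causally related. Three serious AEs judged probably related halt study agent without any test. Section 8 has the DSMB review AE frequency and discontinuations, and lets it act on an indication of harm. The termination wording also concerns severe or serious AEs, not the moderate-or-worse group used in the illustration.
- **That no effect estimate is available.** Section 10.4.4 plans per-condition descriptive statistics. The mean of a yes/no variable is a proportion, so a crude difference can be read off. What is missing is a stated difference with its interval.
- **That non-significance will be reported as safety.** No passage says so. It is a reading that the plan leaves open.

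Three further objections carry weight. The miss rates depend on assumed AE rates, test and correlation, and other reasonable choices bring them below one half. Worsening suicidality, the gravest concern in this population, is also the primary outcome, measured daily and tested two-tailed, so it does not rest on the binary AE test alone. Finally, an interval does not raise power: a study of 30 completers will be imprecise on AEs however they are reported.

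The DSMB can also ask for the tables it wants (section 8), and its charter, still to be written, will define the data elements (section 8.6). That offers a route for the fix, but it does not put the fix in the plan.

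**Conclusion.** The point holds as a gap in analysis and reporting. The only stated inferential comparison of AEs between conditions is a .05 test. No between-condition difference or interval is planned, and no power is stated. Under the assumed 10% v 30%, 30 pairs miss the excess about 54–64% of the time with an exact two-sided McNemar test at correlations of 0 to .3, and 37–54% with mid-p or uncorrected tests. These figures illustrate scale and do not predict this trial's AE rates. The result for 5 pairs needs no assumption about rates, only that the test is exact and two-sided. A non-significant AE comparison is therefore weak evidence of no harm. The change is worth making because it alters what the trial can say about safety at almost no cost.

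**What to change.** In sections 10.4.4, 8.5 and 10.4.7.1, and in the matching text of 5.5:

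- For each AE severity class, at each six-monthly review and at the end, report the within-woman risk difference (active minus placebo) with a 95% confidence interval. Name a paired method suited to small samples, such as a score-based or exact paired interval, not Wald.
- State that non-significance will not be reported as evidence of no increased risk. Describe the safety result by what the interval does and does not exclude.
- Keep the p-value, if wanted, as a descriptive item, and name the test and its sidedness. Leave any tolerable excess to the DSMB charter.

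The halting rule, causality judgement and DSMB review are not altered by this. The cost is protocol and charter wording plus a few table columns from AE data already collected, with no extra participants or procedures. The downside is wide intervals and a more guarded safety statement.

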***Below, we list the adverse events that are most likely to occur in the course of the study***

***and will therefore be monitored most closely (at every daily and weekly participant contact during administration of study agents). However, participants will have the opportunity to report any other adverse event in addition to those listed below.***

### **GENERAL ADVERSE EVENTS**

- Significant deterioration in mood
- Significant deterioration in suicidality
- Any adverse event related to venipuncture
- Any adverse event related to emotional or behavioral reactions to interviews, questionnaires, or tasks

### **ESTRADIOL PHYSICAL SIDE EFFECT ADVERSE EVENTS**

**The most frequent side effects associated with estradiol use include:**

- breast tenderness (occurs in 29% of patients)
- abdominal cramps (occurs in 16% of patients)
- headache (occurs in 13% of patients)
- edema (swelling) (occurs in 10% of patients)
- nausea (occurs in 6% of patients)
- acne (occurs in 3 – 12% of patients)
- skin rash or irritation may also occur at site where the patch is placed (occurs in 3 - 12% of patients)

**Rare side effects (<1%) include:**

- jaundice (yellowing of skin)
- increased blood pressure
- worsening of migraines or asthma
- enlargement of uterine fibroids
- intolerance to contact lenses
- dizziness
- changes in appetite and weight

### **PROGESTERONE PHYSICAL SIDE EFFECT ADVERSE EVENTS**

**The most common side effects associated with progesterone include:**

- breast tenderness (occurs in 16% of patients)
- dizziness (occurs in 24% of patients)
- abdominal cramping (occurs in 20% of patients)
- headache (occurs in 16% of patients)
- viral infection (occurs in 12% of patients)
- joint pain (occurs in 12% of patients)
- diarrhea (occurs in 8% of patients)
- menstrual bleeding, sometimes consistent with a heavy menstrual period (occurs in 20-30% of patients)
- drowsiness (occurs in 9% of patients)

**Rare (<1%) side effects include:**

- vaginal discharge
- chest pain
- abdominal bloating

#### 10.4.5 ADHERENCE AND RETENTION ANALYSES

Adherence to hormone administration protocols will be characterized following the close of the study using serum assays for E2 and P4 during the active condition relative to hormonal profiles during the placebo condition; it will not be monitored in real time.

Women will be monitored in their compliance daily during each study condition via a phone call with study staff. Any deterioration in adherence will be immediately remedied via increased reminders and phone calls.

#### 10.4.6 BASELINE DESCRIPTIVE STATISTICS

Groups (counterbalanced order as placebo-experimental or experimental-placebo) will be compared on demographic factors such as age, severity of perimenstrual mood change in the placebo condition, and general suicidality. However, inferential statistics are not necessary as our primary outcome modeling procedures will control for any baseline differences that exist.

#### 10.4.7 PLANNED INTERIM ANALYSES

##### 10.4.7.1 SAFETY REVIEW

At six month intervals, the study biostatistician ([name]) will test whether there are significant differences in the occurrence of moderate, severe, and serious AEs in the placebo vs. the experimental condition with alpha set at .05. These results will be provided to DSMB along with the summary report of enrollment.

Administration of study agent will be halted when three serious AEs\* determined to be “probably related” are observed. The PI will immediately notify the DSMB when this occurs. The DSMB will notify the study sponsor and investigators immediately when the third severe event is reported and enrollment screens will stop accepting new study participants. [name] will again perform an unblinded statistical analysis to further determine whether active study medication (E2/P4) is significantly related to greater risk of AEs relative to placebo. All requested documentation will be provided to the DSMB. The DSMB will convene an ad hoc meeting by teleconference or in writing as soon as possible. The DSMB will provide recommendations for proceeding with the study to the PI and the NIH. The study sponsor will inform all appropriate regulatory agencies of the temporary halt and the disposition of the study.

The DSMB will consider stopping the entire study based on the results of the statistical tests provided by [name]: specifically, if the experimental hormone stabilization condition is associated with greater risk of severe or serious AEs than placebo, and there is evidence (as determined by follow up with [name] using unblinded data provided by [name]) that such AEs are causally related to the study drug, the study will be terminated.

**\*Notable examples of serious adverse events in the present study include development of a venous thromboembolism or suicide attempt.**

#### 10.4.7.2 EFFICACY REVIEW

There are no efficacy endpoints in the present study because this is not a treatment study and the intervention used is not expected to be an effective treatment for any condition.

#### 10.4.8 ADDITIONAL SUB-GROUP ANALYSES

The study is not powered to conduct sub-group analyses, and therefore they will not be performed.

#### 10.4.9 MULTIPLE COMPARISON/MULTIPLICITY

N/A

#### 10.4.10 TABULATION OF INDIVIDUAL RESPONSE DATA

Individual response data will be tabulated only if requested by the DSMB.

#### 10.4.11 EXPLORATORY ANALYSES

Not applicable.

### 10.5 SAMPLE SIZE

An unlimited number of women will be screened. 45 women will be enrolled in the study, with the goal of 30 women completing the study.

Power analyses are described below; alpha is set at .05, power at 80%. The null hypothesis is no link between the study experimental condition and risk for suicidal ideation, intent, and planning; the alternate hypothesis is that hormone stabilization in the experimental condition will prevent flux in these suicide-related outcomes. Because no previous studies have examined the impact of experimental hormones on suicidality, we have conducted power analyses using existing effect sizes on related constructs (e.g., BPD features).

**Power Analysis.** For the contrast testing the primary hypothesis, we will have power to detect a conventionally medium-sized effect of hormone withdrawal ( $r = .30$ ;  $d = .60$ ) at 80% power with just 17 participants. The PI's previous work in women with BPD suggests that attrition could be as high as 25% across two conditions; should attrition be this high, enrollment of 22 participants would be required for adequate power. However, to improve generalizability of our findings and to ensure 80% power to detect small-to-medium effect sizes ( $r = .20$ ;  $d = .40$ ), we aim to include 30 completers (with 45 women randomized). This number is especially reasonable given the

much larger effects found in the candidate's recent studies for the effect of natural ovarian steroid changes (average  $r = .58$ ;  $d = 1.38$ ) on daily symptoms of depression, rejection sensitivity, anxiety, and impulsivity.

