#### 6.1.9 DURATION OF THERAPY

The planned duration of active treatment is 14 days. All days in which participants use patches and pills will be utilized in multilevel modeling analyses, which accommodate unbalanced/missing data.

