### 10.3 ANALYSIS DATASETS

An intent-to-treat dataset will be utilized. The study statistician will use a carry-forward approach to evaluate the within-person condition effect using this intent-to-treat sample.

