#### 10.4.2 ANALYSIS OF THE PRIMARY EFFICACY ENDPOINT(S)

Primary and secondary endpoints are operationalized above (i.e., mean within-person differences between placebo and experimental in final seven days of manipulation) for the daily SITB suicidal ideation and planning subscales (primary endpoints) as well as the daily UPPS-P impulsivity, PROMIS anxiety, CESD depression, BHI hopelessness, and SSES rejection sensitivity subscales (secondary endpoints).

**Analyses will proceed identically for all outcomes listed above.** First, we will calculate each subject's mean daily rating (via phone) on the outcome measure *in the final seven days of both the placebo condition* (placebo mean score) and the experimental condition (experimental mean score).

Second, we will utilize paired samples t-tests to examine the within-person condition effect. If proposed covariates (medicines, BMI, age) show sufficient variability, we will instead use a repeated measures ANCOVA to evaluate the condition effect. These analyses will be conducted on the intent-to-treat dataset.

If necessary due to violations of model assumptions, we will utilize similar nonparametric tests.

---

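### The 80% power in Section 10.5 does not reproduce for the planned two-tailed paired t-test: it is 64% and 56% if d is scaled by the SD of differences, and no other scaling is stated

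*Combined protocol and SAP*

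**What the plan says.** Section 10.5 (Sample Size) sets alpha at .05 and power at 80% and makes two claims:

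- An effect of r = .30, d = .60 is detectable "at 80% power with just 17 participants". With 25% attrition, "enrollment of 22 participants would be required for adequate power".
- The aim is 30 completers out of 45 randomised, "to ensure 80% power to detect small-to-medium effect sizes", given as r = .20, d = .40.

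The analysis is described elsewhere:

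- Section 10.4.1: "Primary hypothesis tests will be evaluated using a alpha level of .05, with a two-tailed test".
- Section 10.4.2, after forming each woman's mean over the final seven days of each condition: "Second, we will utilize paired samples t-tests to examine the within-person condition effect". A repeated measures ANCOVA replaces this if the covariates vary enough, and nonparametric tests if assumptions fail.
- Section 10.3: "The study statistician will use a carry-forward approach to evaluate the within-person condition effect using this intent-to-treat sample".
- Section 6.1.9: "All days in which participants use patches and pills will be utilized in multilevel modeling analyses".

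Section 10.5 gives no SD of the differences, no correlation between the two condition means, no definition of d and no number of repeated measures. Support for the figure of 17 is a textbook citation. Section 10.1 says that there will be no formal SAP, so no later document is planned to supply these inputs.

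**The concern.** The power of a paired t-test depends on the mean difference relative to the SD of the within-woman differences. A value of d can be used only if the reader knows that it is scaled that way, or knows the correlation that converts it. Section 10.5 gives neither, and the most direct reading gives power well short of 80% in both scenarios.

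The study is meant to support or refute a causal role of hormone withdrawal, so a null result will be read against the claim of 80% power for a small-to-medium effect. If d is d_z, the chance of missing d = .40 with 30 completers is about 44% (1 − 0.56), not 20%. If d uses the raw-score SD, that chance depends on a correlation that the plan does not state. A reader cannot tell which applies.

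**Working it through.** **Inputs.** Two-tailed alpha .05 (Section 10.4.1); paired t-test on two 7-day means (Section 10.4.2); n = 17 with d = .60 and n = 30 with d = .40 (Section 10.5).

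**Formula.** With n pairs, df = n − 1 and noncentrality δ = d_z·√n. Power = P(|T| > t_{.975, df}), where T is noncentral t with parameter δ.

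**1. The plan's figures, with d read as d_z.**

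- n = 17, d_z = .60: δ = .60·√17 = 2.474, critical value 2.120, power **0.642** (stated: 0.80).
- n = 30, d_z = .40: δ = .40·√30 = 2.191, critical value 2.045, power **0.563** (stated: 0.80).
- Smallest n for 80%: **24** at d_z = .60 and **52** at d_z = .40.
- Smallest d_z detectable at 80%: 0.724 with 17, **0.529** with 30, 0.427 with 45.
- With 30 completers and d_z = .60, power is 0.888. With d_z = .40 and all 45 women contributing both conditions, it is 0.747.

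**2. Other calculations that might lie behind the claim (n = 17, d = .60 / n = 30, d = .40).**

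| Variant | Power |
|---|---|
| One-sided t | 0.765 / 0.690 |
| Two-sided normal approximation | 0.696 / 0.591 |
| One-sided normal approximation | 0.796 / 0.707 |
| Repeated-measures ANOVA, two conditions, correlation .5 | 0.642 / 0.563 |
| Wilcoxon, approximated by relative efficiency 0.955 | about 0.61 / 0.55 |

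Converting the stated r by d = 2r/√(1 − r²) gives .629 and .408; the two-sided t-test then needs 22 and 50 women. Only the one-sided normal approximation comes near 80% for 17 women at d = .60. It contradicts the two-tailed test and still fails for 30 completers at d = .40.

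**3. d scaled by the raw-score SD.** Then d_z = d/√(2(1 − ρ)), where ρ is the correlation between a woman's two condition means.

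| ρ | Power, d = .60, n = 17 | Power, d = .40, n = 30 |
|---|---|---|
| .5 | 0.642 | 0.563 |
| .6 | 0.738 | 0.658 |
| .7 | 0.850 | 0.780 |
| .75 | 0.907 | 0.850 |
| .8 | 0.956 | 0.917 |

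80% is reached at ρ = 0.656 for 17 women at d = .60 and at ρ = 0.714 for 30 completers at d = .40.

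**4. Do the two sizes fit each other?** If both d values share one scaling, their ratio as d_z is .60/.40 = 1.5 whatever the scaling is. The effects detectable at 80% with 17 and 30 women stand in the ratio 0.724/0.529 = 1.37, so the two sizes cannot both be exact requirements. In terms of ρ:

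- 17 is the smallest adequate n at d = .60 only for ρ from 0.656 to 0.680. In that range 30 completers give 0.724 to 0.753 at d = .40, and 36 to 34 are needed.
- At ρ = 0.714, where 30 completers reach 80% at d = .40, 15 women suffice at d = .60, not 17.

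**5. Does carry-forward recover power?** Section 10.3 does not say what is carried forward. Assume that 15 of 45 women have condition 1 carried into condition 2, giving a difference of zero. Simulating 200,000 trials with 30 differences from N(.40, 1) plus 15 zeros gives power of about 0.56, the same as for completers alone.

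**6. Attrition.** 17/.75 = 22.7, which rounds up to 23; the stated 22 matches 17 × 1.25 = 21.25 rounded up. This slip is minor. If 17 becomes 24, the enrolled number becomes 24/.75 = 32.

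**The case against.** The plan never says that d is d_z. Each d is paired with an r (.30/.60, .20/.40), roughly as the usual conversion would give, so d may have been translated from r and not computed from paired differences. Two 7-day means from the same woman could correlate at .71 or more, and then both 80% statements are true. The power model may also have been a multilevel one: the citation is to a longitudinal analysis text, and Section 6.1.9 mentions multilevel models. Section 10.4.1 expects nonparametric tests, so paired-t power is itself only a guide. Section 10.5 gives 30 partly for generalisability, and cites much larger effects (d = 1.38) from related work.

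Much of this stands. The true power is unknown, and 64% and 56% are results under one reading. But no correlation, variance or multilevel power model is stated, so none of these routes lets a reader reproduce 80%. The high-correlation route leaves the sizes in conflict, because Section 10.5 treats 17 as a requirement when it inflates it to 22. A nonparametric test does not help: the Wilcoxon approximation is slightly lower. The larger cited effects bear on whether 30 is enough in practice, not on whether the claim for d = .40 is right.

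**Conclusion.** The concern holds. For the test that the plan names, 80% power does not follow from the stated inputs. With d read as d_z, power is 64% (17 women, d = .60) and 56% (30 completers, d = .40). With the raw-score SD, 80% depends on an unstated correlation of at least .66 and .71 respectively. If one scaling applies to both claims and 17 is the minimum for the first, 30 completers fall short for the second, at 72 to 75%.

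The calculations assume normally distributed differences and one complete pair per woman. They do not prove that the trial is underpowered. On the d_z reading, 30 completers still give 89% power at d = .60.

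**What to change.** Keep 45 enrolled and 30 completers. In Section 10.5, state the standardiser of d, the test and its sidedness, and restate the power.

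*If d is d_z*, suggested wording:

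> With 30 completers, a paired t-test (two-tailed, .05) has 80% power for d_z of about 0.53. Power is 89% at d_z = .60 and 56% at d_z = .40 (75% if all 45 women have data in both conditions).

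Then replace 17 by 24, and 22 by 32.

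*If d uses the raw-score SD*, state the assumed within-woman correlation between the two 7-day means and its source, and recompute both sample sizes from that one value.

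*If a multilevel model was used for the power calculation*, state its variance assumptions and reconcile it with the paired t-test in Section 10.4.2.

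The cost is wording in Section 10.5. The stated power will probably look less favourable. No extra women are needed, and neither conduct nor analysis changes.
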